Study visit day -7: Meal challenge test: In order to assess the changes induced by liraglutide, a meal challenge will be carried out prior to and following liraglutide (week 0 and week 26): a 910 calorie high fat high carbohydrate meal will be given, as in several of our previous papers(20).Bolus dose will be given at 3-4 hours after the ingestion of the meal based on the blood sugar and correction factor for each individual subject as giving bolus insulin immediately before meal may confound the true effects of liraglutide. Acetaminophen (1000 mg for body weight <125lbs, 1250 mg for body weight 125-150 lbs, 1500 mg for body weight 151-175 lbs and 1750 mg for body weight >175 lbs) will be ingested at the beginning of the meal, and the blood levels of acetaminophen will be determined at intervals for assessment of the rate of gastric emptying. Liraglutide will be injected only at week 26 (45 min prior to the meal). Sequential blood samples will be obtained at 0, 15, 30, 45, 60, 90, 120, 150, 180, 210, 240 and 300 min. Samples at 15, 30, 45, 90, 150 and 210 min will be 5 ml while those at 0, 60, 120, 180, 240 and 300 min will be 30 ml (total volume=210 ml). Blood will be collected from an indwelling intravenous canula in a superficial forearm vein.

Study visit day -1: Subjects will come fasting for this visit. Records of blood glucose concentrations monitored by fingerstick and CGM for the previous 14 days will be obtained to assess their glycemic control prior to liraglutide treatment (**this will serve as the baseline assessment of mean blood glucose for the study**). The subjects will have their 24 hour blood pressure measurements completed. Brachial reactivity will be assessed by measuring by flow mediated dilation (FMD). They will undergo a meal challenge test (described below) and a fat biopsy. 24 hr urine will be collected.

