Study Visit day 0: Subjects will come fasting for this visit. Each subject will be given one injection of Liraglutide 1.2 mg or placebo. A fructosamine and blood samples will be collected at baseline. Blood samples will be collected after the baseline at 30, 60, 120, 180, 240 and 300 minutes after the injection. (**This is being done to evaluate the acute effect of a single injection of Liraglutide on oxidative stress and inflammatory mediators, before any adjustments of insulin dose or effect of Liraglutide on blood glucose and weight is evident**). Subjects will be instructed by the study staff in the dosing and administration of the study medication. They will start Liraglutide injection at a dose of 0.6 mg per day or placebo injection on the following day. We will adjust the doses of basal and bolus insulin to eliminate low blood sugars(less than 70 mg/dl). At all subsequent visits insulin doses will be titrated to target blood sugars between 70-180 mg/dl at all times. Patients will return to the center after 7 days.

Study Visit week 1: Blood glucose concentrations will be reviewed. Insulin dose will be adjusted at the discretion of the study investigator to optimize blood sugar control as per

the targets mentioned above. Patients will be advised to increase the Liraglutide dose to 1.2 mg a day if they are able to tolerate the 0.6 mg dose. If they are experiencing mild nausea, subjects will continue with 0.6 mg daily for another 7 days. Those with severe nausea/vomiting will be dropped from the study. All other subjects will return in 7 days.

Study Visit week 2: Blood glucose concentrations will be reviewed. Insulin dose will be adjusted if needed. Subjects taking 0.6 mg dose and experiencing significant nausea will be dropped from the study. Subjects on 1.2 mg and experiencing significant nausea will decrease the dose to 0.6 mg and continue that dose for the duration of the study. Subjects on 1.2mg and experiencing mild nausea will continue on 1.2 mg for 2 more weeks. Subjects on Liraglutide 1.2mg daily without any gastro-intestinal side-effects will be asked to increase the dose to 1.8 mg daily. Study drug will be dispensed for additional 2 weeks.

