Study Visit week 26: Subjects will come fasting for this visit. Research labs, CBC, CMP, Lipids, HbA1c and fructosamine will be collected. Records of blood glucose concentrations monitored by finger-stick and CGM for the previous 14 days will be obtained to assess their glycemic control. They will undergo meal challenge test (described above) and a fat biopsy. 24 hr urine will be collected. FMD and 24hr blood pressure will be performed. After this visit, subjects will be discharged from the study.

Blood samples (collected in protease and DPP-IV inhibitors) will be appropriately processed and assayed for glucose, C-peptide, glucagon, GLP-1 and gastric inhibitory peptide (GIP) which is also called gastric insulinotropic peptide, Reactive oxygen species (ROS) generation, Thiobarbituric acid reducing substances (TBARS), urinary isoprostanate,

intranuclear nuclear factor kappa B (NFkB) binding, the expression and concentration of Toll like receptor-4 (TLR-4), tumor necrosis factor alpha (TNF α), Inhibitor kappa B (IkB α), Matrix metalloproteinase 9 (MMP-9), Suppressor of cytokine signaling-3 (SOCS-3), Protein kinase C (PKC β II), Phosphotyrosine phosphatase -1B (PTP-1B), Glycogen synthase kinase 3 beta (GSK-3 β), Inhibitor kappa kinase (IKK β), C-jun amino terminal kinase (JNK-1) and amount of Insulin receptor (IR- β) and p-IR β in MNC and plasma concentrations of C-reactive protein (CRP), Monocyte chemoattractant protein -1 (MCP-1), Plasminogen activator inhibitor -1 (PAI-1), TNF α and Regulated upon activation Normal T cell Expressed and Secreted (RANTES). Adipose tissue samples will be processed and analyzed for intranuclear NFkB binding, the expression and concentration of TLR-4, TNF α , IkB α , MMP-9, SOCS-3, PKC β II, PTP-1B, GSK-3 β , IKK β , JNK-1 and amount of IR- β and p-IR β .

Clinical and Laboratory Procedures

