25.0 Compensation for Participation

25.1 Describe the amount and timing of any compensation to subjects, including monetary, course credit, or gift card compensation.

Response:

700.00 after completion of all study visits and procedures:-

- \$50 for study visit day 1,
- \$50 for each fat biopsy,
- \$50 for each meal challenge,
- \$50 for each 24 hour blood pressure monitoring
- \$25 for blood draw (week 12)
- \$15 for each urine sample
- \$15 per visit (for visits 1, 2, 4, 8, 16, 20 and 24)
- \$15 for each DEXA scan
- \$25 for each MRI
- \$15 for each brachial reactivity study

N/A: This study is not enrolling subjects, or is limited to records review procedures only. This section does not apply.

N/A: There is no compensation for participation. This section does not apply.

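### Section 10.1 schedules the baseline meal challenge at both day -7 and day -1, while its own description and the payment total point to a single baseline test

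*Combined protocol and SAP*

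**What the plan says.** Section 10.1 lists the visits in order.

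- **Day -7.** The challenge is the only procedure under this heading: "Study visit day -7: Meal challenge test: In order to assess the changes induced by liraglutide". The same paragraph contains the only description of the test and dates it differently: "a meal challenge will be carried out prior to and following liraglutide (week 0 and week 26". It adds that the insulin bolus is held back for 3 to 4 hours after the meal, that acetaminophen is taken with the meal, and that study drug is injected 45 minutes before the meal at week 26 but not at baseline. On blood volume it says that "those at 0, 60, 120, 180, 240 and 300 min will be 30 ml (total volume=210 ml".
- **Day -1.** "They will undergo a meal challenge test (described below) and a fat biopsy". The description referred to stands above this entry, not below it. The day -1 entry also collects the previous 14 days of fingerstick and CGM records and makes them the baseline for mean glucose.
- **Day 0.** Subjects attend fasting. "A fructosamine and blood samples will be collected at baseline", and timed samples follow the first injection. The stated purpose is to "evaluate the acute effect of a single injection of Liraglutide on oxidative stress and inflammatory mediators".
- **Week 26.** "They will undergo meal challenge test (described above) and a fat biopsy". The visit also includes fasting research labs and the previous 14 days of glucose records.

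Section 25.1 pays $50 "for each meal challenge" within a stated total of $700. Section 17.1 makes the reduction in AUC after the meal a secondary endpoint. It plans between-group and within-group comparisons of change from baseline, but does not say which visit supplies the meal-test baseline. There is no schedule-of-events table to settle the question.

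**The concern.** The visit text is what site staff work from. Read literally, it produces two meal challenges before treatment. Four aims rest on the baseline challenge: postprandial glucose (1.2), glucagon and C-peptide (2.1), the inflammatory response to the meal (3.2) and gastric emptying (5.1). With two tests and no named baseline, the analyst could use the first, the second or their average, and could choose after seeing the data. Patients would also undergo a burdensome test that the rest of the document does not seem to intend.

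A related gap concerns the inflammatory markers. Aim 3.1 compares values before and after (a) a single injection and (b) 26 weeks of treatment, without saying which sample is the earlier one in each comparison. If day -1 is the true date, the day 0 fasting sample is drawn the day after a 910-calorie high-fat, high-carbohydrate meal and a fat biopsy. If day -7 is the true date, only the biopsy comes the day before, but the challenge then lies inside the 14-day glucose baseline window.

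**Working it through.** **1. How many challenges does the payment total allow?** The unit payments are from section 25.1 and the counts from section 10.1.

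| Item | Count | Unit ($) | Sum ($) |
|---|---|---|---|
| Visit listed as day 1 | 1 | 50 | 50 |
| Fat biopsy (day -1, week 26) | 2 | 50 | 100 |
| 24-hour blood pressure (day -1, weeks 12 and 26) | 3 | 50 | 150 |
| Week 12 blood draw | 1 | 25 | 25 |
| Urine sample (day -1, weeks 12 and 26) | 3 | 15 | 45 |
| Visits 1, 2, 4, 8, 16, 20, 24 | 7 | 15 | 105 |
| DEXA | 2 | 15 | 30 |
| MRI | 2 | 25 | 50 |
| Brachial reactivity (day -1, weeks 12 and 26) | 3 | 15 | 45 |
| **Subtotal without meal challenges** | | | **600** |

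Total = 600 + 50 × (number of challenges).

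- Two challenges: 600 + 100 = 700, which reproduces the stated figure.
- Three challenges: 600 + 150 = 750, which is $50 over.

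The sum treats the day 1 item as a single $50 payment, because section 10.1 has no visit of that name. It is strong evidence but not proof. Three challenges could still reach $700 if another $50 item that section 10.1 schedules had been left out.

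**2. Blood volume.** One test: 6 × 5 ml + 6 × 30 ml = 30 + 180 = 210 ml, as stated. Tests at both day -7 and day -1: 2 × 210 = 420 ml within about a week.

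**3. The readings side by side.**

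| Reading | Meal-test baselines | Day before the day 0 sample | Challenge relative to the 14-day glucose window |
|---|---|---|---|
| Both dates | two, no rule for choosing | meal and biopsy | one inside, one at the closing visit |
| Day -1 only | one | meal and biopsy | at the closing visit, as at week 26 |
| Day -7 only | one | biopsy only | inside, unlike week 26 |

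The glucose window is a small matter. The test lasts 300 minutes, or 5 hours, and 14 days contain 14 × 24 = 336 hours. The test period is 5/336 = 1.5% of the window, assuming continuous recording throughout. The 14-day mean would therefore move by about 1.5% of the average excess glucose during those hours.

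**4. Pairing samples for Aim 3.1b.** It is tempting to pair the 0-minute sample of the baseline challenge with the 0-minute sample at week 26. If time 0 is the start of the meal, as the sampling times suggest, the week 26 sample is drawn about 45 minutes after an injection and the baseline sample after none. The day 0 series starts looking for an acute effect at 30 minutes. Such a pairing could mix the acute effect into the 26-week effect, and only in the liraglutide arm.

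**The case against.** The best reply is that this is a drafting slip with little effect on inference. The description names two occasions in all, there is only one description, the day -1 entry points to it in the wrong direction, and the payment total fits two challenges. On that view nobody planned a repeat test, and the extra blood, the extra acetaminophen dose and the choice of baselines arise only on a reading that the document's own figure contradicts. Most of this stands. The point is best put as two dates for what appears to be one test. It does not remove the need for correction, because staff follow visit entries and nothing in the text settles the date.

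A reader might also infer that the meal and biopsy before day 0 confound the inflammatory results. The documents do not support that for liraglutide against placebo. Both randomised arms follow the same pre-treatment schedule, and section 2.1 defines the secondary endpoints as change compared with placebo. Carry-over could matter for the within-group tests in section 17.1, but no figure is given for how long either effect lasts, so it cannot be sized. The meal falls on the day before day 0 only if a challenge is held on day -1. Section 10.1 also ties the day 0 series to the acute effect and does not make it the baseline for the 26-week comparison.

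**Conclusion.** The schedule is wrong as written. Section 10.1 orders the baseline meal challenge at two visits and gives it a third label, week 0, while its own description and the $700 total support one baseline test and one at week 26. Followed literally, it costs each patient one unneeded challenge: 210 ml more blood (420 ml in place of 210 ml), a second acetaminophen dose and a second delayed bolus. It also leaves Aims 1.2, 2.1, 3.2 and 5.1 with two possible baselines and no rule.

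The inference that one test was intended rests on the payment counts above and on the description's wording. Which date was meant cannot be settled from the documents. The week 26 wording, which puts the challenge and the biopsy at one visit, resembles the day -1 entry, but that is only suggestive.

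The effects are confined to secondary endpoints. HbA1c and the sample size are untouched, and any carry-over into day 0 is common to both arms and bears only on within-group comparisons.

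**What to change.** 1. In section 10.1, reconcile day -7, day -1 and week 0 to one baseline challenge, and correct the cross-reference in the day -1 entry. The investigators must decide the date. If the challenge stays inside the 14-day glucose window, section 17.1 should say how that day is handled, because at week 26 the challenge comes at the visit that closes the window.
2. In section 17.1, name that visit as the baseline for all meal-test endpoints.
3. In section 17.1, state that the day 0 pre-injection sample is the baseline for the acute comparison (Aim 3.1a).
4. In section 17.1, state that the 26-week comparison (Aim 3.1b) uses fasting samples drawn, at both times, before any study-drug injection that day. The 0-minute meal sample at week 26 should not serve for this. The fasting research labs already planned at week 26 can, once their timing before the injection is written down.

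The cost is a few lines of wording. No samples or visits are added, and each patient may be spared one test.

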8.0 Eligibility Screening

8.1 Describe screening procedures for determining subjects' eligibility.

Screening refers to determining if prospective participants meet inclusion and exclusion criteria.

- Include all relevant screening documents with your submission (e.g. screening protocol, script, questionnaire).

Response: :

Prospective participants will be asked to read and understand the consent and any questions they may have regarding the protocol will be answered. If the subject wants to participate in the study, they will be asked to sign the informed consent form. The subject's medical history and current medications will be obtained as well as their blood pressure and vitals. A physical examination will also be done. Fasting labs before 10:00am include; CBC, CMP, HbA1c, lipid panel, C-peptide and GAD-6 and a urine pregnancy test. Blood samples of patients with negative GAD-65 antibodies will be screened for islet cell antibodies, if patient had evidence of auto- immunity to beta cells in the past, they will be retested during screening. Patients with no evidence of autoimmunity to beta cells will not be included in this trial. Patients meeting all the inclusion and exclusion criteria based on all screening tests will be enrolled in the study.

- N/A:** There is no screening as part of this protocol.

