Study Visit week 4: Subjects will be asked to bring in their used study pens and the pen that they are using so that study nurse can log in the amount of drug used. If needed, the dose will be increased. The goal in the first 4 weeks is to increase patient's liraglutide dose to maximum tolerated dose. Maximum dose of liraglutide will be 1.8 mg daily. Subjects experiencing mild nausea with 0.6 mg or 1.2 mg will continue at that dose in the study. Those with severe nausea/vomiting with 1.8mg will decrease their dose to 1.2 mg and continue that dose throughout the study. Blood glucose concentrations will be reviewed. Insulin dose will be adjusted if needed. CGM will be discontinued. Study drug will be dispensed to last till the next visit.

Study visit week 8: Subjects will be asked to bring in their used study pens and the pen that they are using so that study nurse can log in the amount of drug used. Blood glucose concentrations will be reviewed. Insulin dose will be adjusted if needed. Study drug will be dispensed to last till the next visit.

Study Visit week 12: Subjects will be asked to bring in their used study pens and the pen that they are using so that study nurse can log in the amount of drug used. Blood glucose concentrations will be reviewed and vascular activity will be performed. Insulin dose will be adjusted if needed. Fasting blood, research labs, HbA1c, fructosamine, lipid panel, urine pregnancy test and 24 hr urine will be collected. FMD and 24hr blood pressure will be studied. Study drug will be dispensed for additional 4 weeks.

Study Visit week 16 and 20: Subjects will be asked to bring in their used study pens and the pen that they are using so that study nurse can log in the amount of drug used. Blood glucose concentrations will be reviewed. Insulin dose will be adjusted if needed. Study drug will be dispensed for additional 4 weeks.

Study visit week 24: CGM will be inserted. They will have their body composition measured by DEXA and MRI prior to next visit.

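### Urine pregnancy tests are listed only at screening and week 12: none is repeated before the first injection, and none falls in the last 98 of 182 dosing days

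*Combined protocol and SAP*

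**What the plan says.** The visit narrative in section 10.1 is the only schedule; the protocol has no schedule-of-events table. Read visit by visit, it names a urine pregnancy test twice.

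- **Screening** (8.1, repeated in 10.1): the laboratory list ends with "C-peptide and GAD-6 and a urine pregnancy test".
- **Week 12** (10.1): "Fasting blood, research labs, HbA1c, fructosamine, lipid panel, urine pregnancy test and 24 hr urine will be collected".

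The visits around the two gaps list other procedures and no pregnancy test.

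- **Day -1:** "a meal challenge test (described below) and a fat biopsy. 24 hr urine will be collected". The urine assay described in 10.1 is for isoprostane.
- **Day 0:** "Each subject will be given one injection of Liraglutide 1.2 mg or placebo. A fructosamine and blood samples will be collected at baseline".
- **Weeks 16 and 20:** "Study Visit week 16 and 20: Subjects will be asked to bring in their used study pens", followed by glucose review, insulin adjustment and dispensing.
- **Week 24:** "Study visit week 24: CGM will be inserted", with DEXA and MRI to follow.
- **Week 26:** "Research labs, CBC, CMP, Lipids, HbA1c and fructosamine will be collected".

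Dosing runs to the end: for the meal challenge, "Liraglutide will be injected only at week 26 (45 min prior to the meal". Pregnancy is an exclusion criterion (6.2), a ground for withdrawal (20.1) and a trigger for immediate withdrawal (21.4). Section 21.4 also requires a signed commitment to at least two forms of birth control. Section 19.5 provides for safety data at every visit and same-day review of events reported by phone.

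**The concern.** Exclusion and immediate withdrawal protect a participant only if the pregnancy is known. Followed exactly, the schedule gives the first 1.2 mg injection without rechecking an exclusion criterion last tested at least two weeks before. After week 12, withdrawal depends on the participant recognising and reporting a pregnancy. The plan evidently regards on-study testing as worthwhile, since it tests at week 12 despite the contraception requirement, but it gives no reason for stopping there when more than half of dosing is still to come.

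At stake is delayed detection, and so avoidable dosing during an early pregnancy. The efficacy comparison is not at stake.

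**Working it through.** **Inputs from the documents.** Run-in of 2 weeks and dosing for 26 weeks (11.2); 42 of 84 participants on liraglutide (11.2); first visit after screening on day -14, first injection on day 0, last listed test at week 12 (10.1).

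**Inputs assumed, because the documents give none.** Women of child-bearing potential, n = 20-40; conception rate r = 1-5 per 100 woman-years; screening S = 0, 14 or 28 days before day -14; urine-test detection lag L = 0-14 days; false-positive rate 0.1-1% per test.

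**1. Calendar.** 2 + 26 = 28 weeks, which reproduces the stated participation period. Dosing days = 26 × 7 = 182. Week 12 = day 84. Days after the last test = 182 - 84 = 98, and 98/182 = 53.8%. Counting the day 0 injection as an extra dosing day gives 53.6-54.1%.

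**2. Gap before the first injection.** 14 + S = 14, 28 or 42 days. Only the minimum of 14 follows from the documents.

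**3. Expected conceptions** = n × r/100 × days/364.

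| Period | Low | High | Liraglutide arm (half) |
|---|---|---|---|
| Screening to first injection | 20 × 0.01 × 14/364 = 0.008 | 40 × 0.05 × 42/364 = 0.23 | 0.004-0.12 |
| After week 12 | 20 × 0.01 × 98/364 = 0.05 | 40 × 0.05 × 98/364 = 0.54 | 0.03-0.27 |
| Both | 0.06 | 0.77 | 0.03-0.38 |

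These figures are before dropout.

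**4. What a day 0 test adds.** It newly detects conceptions dated from L days before screening up to day -L. The number of those dates that fall after screening is max(0, 14 + S - L).

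- L = 14: 0, 14 or 28 days for S = 0, 14, 28.
- L = 7: 7, 21 or 35 days.

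With screening on day -14 and a 14-day lag, the day 0 test therefore detects no conception that occurred after screening. It finds only those from the preceding 14 days that the screening test was too early to show. Its value grows with the screening gap, which the protocol leaves unbounded.

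**5. Dosing days after a conception between weeks 12 and 26, if it is never self-reported.** Conception is taken as uniform over days 84-182, and time is counted to the first test at least L days later, or to day 182.

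| Tests after week 12 | L = 0 | L = 7 | L = 14 |
|---|---|---|---|
| None (current plan) | 49 | 49 | 49 |
| Week 24 only | 37 | 38 | 39 |
| Weeks 16, 20 and 24 | 13 | 18 | 23 |

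For example, with weeks 16, 20 and 24 and L = 0: (3 × 28 × 14 + 14 × 7)/98 = 1274/98 = 13.

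**6. Burden.** One pre-dose test plus three on treatment is 4 per woman: 4 × 20 = 80 to 4 × 40 = 160 tests. Expected false positives: 80 × 0.001 = 0.08 to 160 × 0.01 = 1.6.

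**The case against.** The strongest reply is that no rule is broken. Sections 6.2, 20.1 and 21.4 promise no testing interval, and nothing in the documents requires monthly tests. Protection is layered: a screening test, two-method contraception, a mid-study test, contact at every visit and phone reporting. Expected events are below one on every assumed input, and the 49-day figure applies only if a woman stays silent through several visits. The documents give no embryo-fetal data for liraglutide, so harm per exposed day cannot be sized. The contraception commitment sits in the consent, whose pages were removed before review, so additional tests there cannot be ruled out.

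Much of this stands, and it fixes the point as minor. It also rules out two stronger readings that a reader might infer. One is that pregnancy goes unmonitored for 54% of dosing. Safety contact continues throughout that time; what stops is listed testing. The other is that the schedule contradicts the withdrawal rule. It does not; it leaves the rule dependent on self-report after week 12.

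What does not stand is that the other safeguards make testing unnecessary. Contraception lowers incidence but detects nothing. Self-report needs the woman to suspect pregnancy first, and nausea and vomiting are listed as the drug's most common side effects (10.2, 19.2). That masking matters most during dose escalation in the first four weeks and less after week 12.

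**Conclusion.** The point holds as a minor participant-safety gap. Two facts rest on the documents alone: the exclusion is not rechecked in the 14 or more days before the first injection, and no test is listed in the last 98 of 182 dosing days. Everything about event numbers and exposure rests on the assumptions stated above. On those, the two gaps together carry 0.06-0.77 conceptions over both arms, about half of them on liraglutide.

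Confidence is high about what section 10.1 lists. It is lower about whether participants would in practice go untested, because the consent pages could not be checked.

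A reader might also infer a threat to the trial's result. The documents do not support that. Pregnancy already leads to withdrawal, so testing mainly changes when it is found, and with fewer than one expected event the effect on the primary endpoint, power and analysis is negligible.

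**What to change.** Amend section 10.1 for women of child-bearing potential:

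1. Require a negative urine pregnancy test at day -1 or day 0, before the first injection. Urine is already collected at day -1.
2. State a maximum interval between screening and day 0.
3. Add the test at the existing week 16, 20 and 24 visits. The longest gap after week 12 then falls from 98 to 28 days. Adding week 24 alone would cut it only to 84.
4. Repeat any positive result before permanent withdrawal.

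Tests at weeks 4 and 8 are optional. Without them the interval from day 0 to week 12 stays at 84 days; with them the longest on-treatment gap is 28 days throughout. If the consent form already specifies further tests, section 10.1 should be brought into line with it.

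The cost is about four extra urine tests per woman, or 80-160 in total on the assumed numbers, all at scheduled visits with at most a spot sample, plus an occasional false positive (0.08-1.6 expected on the assumed rate). No new visit, invasive procedure or change to the analysis is needed.
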